7.9 WITHDRAWALS AND LOST TO FOLLOW-UP

Participation is completely voluntary, and each subject is free to withdraw from the study at any time. An investigator also has the right to withdraw the subject from the study in the event of reasons concerning the health or well-being of the subject, or in the case of lack of cooperation. Should a subject decide to withdraw for any reason, or should the investigator decide to withdraw the subject, all efforts will be made to complete and report the observations up to the time of withdrawal as thoroughly as possible. A complete final evaluation at the time of the subject's withdrawal must be made and an explanation given as to why the subject is withdrawing or being withdrawn from the study.

The reason for and date of withdrawal must be recorded on the subject's End of Study/Study Exit CRF. If the reason for the withdrawal is a device-related or procedure related AE, the event must be reported to the Sponsor and recorded in the CRF.

If the procedure is aborted, the subject does not need to complete the follow-up assessments, unless the subject is converted to surgical repair. Subjects who require conversion to open surgery due to treatment failure with the device will be followed for safety through 30 days, or until any treatment related adverse events resolve, which ever is later. The subject's enrollment roster position may not be made available to other subjects (i.e., the subject will not be replaced).

All efforts will be made to return subjects for all the follow-up visits. Due diligence in reaching the subject must be made by two documented telephone contact attempts, emails, or regular postal mail letters. After the above attempts are made, if no response is obtained, the final evaluation of the subject will be the last visit at which study-related procedures were performed. The End of Study/Study Exit CRF page will be completed, and communication attempts will be documented.

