8 RISK ANALYSIS

8.1 RISKS TO THE SUBJECTS

The CLOUT Registry involves the use and disclosure of deidentified personal health information. It collects only information relevant to the subject's DVT condition and its treatment.

The Registry study involves the collection of specific information for research and educational purposes only. It does not specify how the ClotTriever Thrombectomy System will be used to treat thrombus, and decisions regarding a subject's treatment are not influenced by the Registry study. Physicians participating in the Registry study are expected to review the indications, contraindications, warnings, precautions, and AEs described in the IFU. As with any endovascular procedure, the treating physician is expected to counsel the subject on the risks and benefits specific to the planned treatment and to obtain procedure-related informed consent per institutional policy and procedure.

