13 ETHICS

13.1 INFORMED CONSENT

Written informed consent will be obtained from each subject prior to the subject's medical record or personal health information being shared with any study representative. The subject's willingness to participate in the study will be documented in writing in a study-specific Informed Consent Form, which will be signed and dated by the subject or Legally Authorized Representative. The Investigator will keep the original consent form and a copy will be given to the subject. It will be explained to the subjects that they are free to refuse entry into the study and free to withdraw from the study at any time without prejudice to future treatment. Subjects will be consented for two years or for the duration of the subject's participation in the study.

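### Two unanswered contact attempts at any visit can end a subject's participation, so loss by 2 years can be cumulative and possibly informative, with no planned handling

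*Protocol*

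**What the plan says.** Protocol Section 7.9 sets the contact effort: "Due diligence in reaching the subject must be made by two documented telephone contact attempts, emails, or regular postal mail letters". It then gives the consequence: "After the above attempts are made, if no response is obtained, the final evaluation of the subject will be the last visit". That means the last one with study procedures. The step is closed administratively: "The End of Study/Study Exit CRF page will be completed, and communication attempts will be documented". The rule is not tied to a particular visit. The text gives no spacing between attempts, no wait for the visit window to close, no alternate contact, no record or vital-status check and no way back in. The same paragraph also commits to trying to bring subjects back for every visit.

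On investigator withdrawal, Section 7.9 says: "An investigator also has the right to withdraw the subject from the study in the event of reasons concerning the health or well-being". Lack of cooperation is a further ground. It adds a safeguard: "A complete final evaluation at the time of the subject's withdrawal must be made", with the reason and date recorded. A device- or procedure-related adverse event that leads to withdrawal must be reported.

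Section 8.1 says of the registry: "It does not specify how the ClotTriever Thrombectomy System will be used to treat thrombus". Section 9.2 calls it purely a data collection study and makes any event resulting in death reportable. On consent, Section 13.1 says: "Subjects will be consented for two years or for the duration of the subject's participation in the study".

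Section 7.6 schedules visits at 30 days, 6 months, 1 year and 2 years, with windows that run without a break from day 14 to day 900. SAP Section 4 imputes missing effectiveness data, which are measured at the index procedure, and otherwise leaves missing values unimputed as a general rule.

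**The concern.** An unanswered round of contact at an early visit is treated as the end of participation rather than as one missed visit. A subject who cannot be reached at 30 days or 6 months can be exited while later windows, the last closing at day 900, are still open. That holds even if the subject later returns to the same clinic for usual care. Non-response that might have been intermittent becomes permanent.

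Withdrawal on health grounds is linked to health by its own wording. The registry assigns no treatment, so this withdrawal changes no treatment; what it ends is data collection.

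Both routes can remove subjects whose outcomes differ from those who stay. The outcomes at stake are the longer-term secondary ones in Protocol Sections 4 and 5.3: patency, rethrombosis, edema, pain, Villalta (and so post-thrombotic syndrome), rVCSS and EQ-5D. Protocol Section 10.5 refers imputation and sensitivity methods to the SAP, but the SAP supplies none for these outcomes. Data that were never collected cannot be recovered at analysis.

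**Working it through.** **The plan's own attrition figure.** The only loss-to-follow-up rate in either document is 5% over 30 days (Protocol Section 10.8, SAP Section 5.1). It reproduces: 86 / (1 − 0.05) = 90.5, rounded up to 91. The exact one-sided binomial power at n = 86 (34% goal, 20% anticipated, alpha 0.025) is 81.5%, against 82% stated. Neither figure depends on 2-year retention. No rate is given for 6 months, 1 year or 2 years, so everything below rests on assumed rates.

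**Scenario 1: unreachable at a visit, so exited.** Let m be the chance that contact fails at each of the four post-discharge visits, equal at each and independent between visits. With exit at first failure, the share with 2-year data is (1 − m)^4. With files kept open it is 1 − m.

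| m | Exit at first failure | of 91 | Files kept open | of 91 |
|---|---|---|---|---|
| 5% | 0.95^4 = 81% | 74 | 95% | 86 |
| 10% | 0.90^4 = 66% | 60 | 90% | 82 |
| 15% | 0.85^4 = 52% | 48 | 85% | 77 |

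At m = 10% the gap is 90.0 − 65.6 = 24.4 percentage points.

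**How far independence drives this.** If exactly the same 10% are unreachable at every visit, both rules leave 90% and the gap is zero. Positive dependence between visits lies between these two cases. The 24.4 points are therefore an upper bound unless failing to reach a subject once makes that subject easier to reach later.

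**Scenario 2: a missed visit triggers exit only if contact also fails.** Let m now be the chance of missing a visit and q the share of misses in which both contact attempts fail. The share missing at 2 years is 1 − (1 − mq)^3 × (1 − m). At m = 10%, again with independence:

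- q = 0: 10.0%
- q = 10%: 1 − 0.99^3 × 0.90 = 12.7%
- q = 25%: 1 − 0.975^3 × 0.90 = 16.6%
- q = 50%: 1 − 0.95^3 × 0.90 = 22.8%
- q = 100%: 1 − 0.90^3 × 0.90 = 34.4%

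The ratio to those who miss the 2-year visit alone runs from 1.0 to 3.4 here, and up to about 3.7 at m = 5%.

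**What selective loss would do.** Assume, for illustration only, a true poor-outcome rate of 20% and total loss of 20%. If poor-outcome subjects are lost twice as often as the others, loss is 0.20 / (0.2 × 2 + 0.8) = 16.7% among the others and 33.3% among them. The rate seen in completers is 0.2 × 0.667 / (0.2 × 0.667 + 0.8 × 0.833) = 16.7%. It is 20.0% if loss is unrelated to outcome, 18.2% at 1.5 times and 14.3% at 3 times.

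**The case against.** A reader might infer that the registry will lose far more subjects than miss the 2-year visit, and the sickest first. The documents support neither. They give no non-response or health-withdrawal rate beyond 30 days and no order of loss. The multiple runs from 1.0 upward depending on assumed inputs, and a missed visit leads to exit only when the contact attempts also fail.

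A reader might also see the two-attempt rule as contradicting the commitment to bring subjects back for every visit. It does not: a stated minimum can sit beside a general aim. The windows are long and contiguous, and nothing obliges a site to complete the exit before a window closes. Equally, nothing tells it to wait.

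Withdrawal has real safeguards: a final evaluation, a recorded reason, adverse event reporting and reportable deaths. They cover the time up to exit. No step looks for events after it. The right to withdraw for health reasons is discretionary, and visits, ultrasound and questionnaires carry some burden, so the documents do not show that it serves no purpose or must be deleted.

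Finally, study success (Protocol Section 10.4) rests on the two primary endpoints, and no hypothesis test is specified for the 2-year outcomes. That limits the consequence; it does not remove the gap.

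**Conclusion.** The point holds as a weakness in the follow-up rule. Followed as written, Section 7.9 can permanently remove a subject from the 1- and 2-year outcomes after as few as two unanswered attempts. Health-based withdrawal adds a route that may depend on outcome, and the SAP plans no handling for either.

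The size is not known. The 66% against 90% figure assumes 10% unreachable at each of four visits, independently; under persistent non-response the difference disappears. One may suspect that long-term results would look better than they are, but that needs loss to be related to poor outcome. The documents make this possible without showing it.

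Technical Success is measured at the procedure and is untouched. The 30-day MAE endpoint is little affected and already has a 5% attrition allowance. The change is worth making because it is cheap and prevents avoidable loss.

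**What to change.** Revise Protocol Section 7.9 as follows.

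- Record an unanswered round of contact as a missed visit, and try again at each later window. Complete the lost-to-follow-up exit only when the 2-year window closes at day 900.
- Where consent allows, have the site check its own records at each missed window for death, rethrombosis, reintervention and bleeding. This will not recover Villalta, rVCSS or EQ-5D.
- For investigator withdrawals, separate stopping visits from ending record-based data collection. Continue the latter unless the subject withdraws that consent.

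The cost is protocol wording, files that stay open longer and brief chart checks. Consent wording must also be confirmed: Section 13.1 refers both to two years and to the duration of participation, day 900 lies beyond two years, and the consent form was not available for this review.

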7.10 COVID-19 EFFECT ON RESEARCH

This Registry study was designed to capture real-world data regarding the clinical use of the ClotTriever System. As a result of the COVID-19 pandemic, clinic practice patterns may have been affected and patient visits may have been postponed or eliminated. In addition, some data may be collected from patients over the phone. Our goal is to collect as much real-world data as possible while protecting everyone's safety. In light of this situation, any deviation from the protocol due to COVID-19 will not be recorded as a protocol deviation (see Section 11.3 for additional information regarding protocol deviations).

8 RISK ANALYSIS

8.1 RISKS TO THE SUBJECTS

The CLOUT Registry involves the use and disclosure of deidentified personal health information. It collects only information relevant to the subject's DVT condition and its treatment.

The Registry study involves the collection of specific information for research and educational purposes only. It does not specify how the ClotTriever Thrombectomy System will be used to treat thrombus, and decisions regarding a subject's treatment are not influenced by the Registry study. Physicians participating in the Registry study are expected to review the indications, contraindications, warnings, precautions, and AEs described in the IFU. As with any endovascular procedure, the treating physician is expected to counsel the subject on the risks and benefits specific to the planned treatment and to obtain procedure-related informed consent per institutional policy and procedure.

8.2 RISK MITIGATION

This Registry study was designed to capture real-world data regarding the clinical use of the ClotTriever Thrombectomy System. The risk of providing this personal health information is believed to be minimal, as information directly identifying the subject will not be collected for the Registry database. All data handling will be in accordance with HIPAA requirements and only deidentified PHI will be used.

9 SAFETY ASSESSMENTS

9.1 Defining Adverse Events

An AE is an untoward medical occurrence or exacerbation of an existing medical condition subsequent to treatment with the ClotTriever. AEs are classified in several ways, including severity, relationship, and seriousness.

- Severity (mild, moderate, severe)
 - *Mild*: No limitation of usual activities, no therapy or only symptomatic therapy required to treat the injury or illness.
 - Moderate: Some limitation of usual activities or specific therapy is required.
 - Severe: Inability to carry out usual activities, hospitalization, emergency treatment, life threatening events, or death.
- Relationships (unrelated, device-related, procedure-related, or relationship unknown)
 - *Unrelated:* The clinical event is completely independent of study procedure/study device and/or evidence exists that the event is definitely related to another etiology.
 - **Device-related:** An event that can be directly attributed to the use of the device, wherein, if the device functioned 100% to specifications and expectations, the event would not have occurred.

- Rethrombosis in the absence of device induced vascular trauma (documented on an imaging study or with direct visualization of the vessel) is not device-related; rather it is a complication related to ineffective anticoagulation therapy.
- Perforation from the study device is device-related, but perforation from a non-study adjunctive device is not.
- As well, events that occur as a result of downstream venous compression (e.g., May-Thurner syndrome) are not considered device-related.
- Procedure-related: An event that is not device-related and occurs as a result of the procedure.
 - Events that occur ≤30 days of the index procedure or ≤30 days of a secondary procedure performed for a previous procedure-related complication, if the event is not device-related.
 - Examples include complications from ineffective anticoagulation (e.g. rethrombosis), excessive
 anticoagulation (e.g. bleeding), or vascular access with a non-study device (e.g. generic sheath,
 guidewire injury); distant complications (e.g. myocardial infarction, pneumonia); or contrastinduced complications (e.g. contrast-induced nephropathy or hypersensitivity reaction).
- Relationship unknown: The relationship to the study procedure/study device is not known.
- Seriousness (serious, non-serious)
 - Serious AE (SAE): An event that meets at least one of the following:

Is fatal or life-threateningResults in persistent or significant disability/incapacityResults in permanent impairment of a body function or permanent damage to a body structure

Results in hospitalization or prolongs a hospitalization and necessitates medical or surgical intervention to preclude permanent impairment of a body function or permanent damage to a body structure

9.2 REPORTING ADVERSE EVENTS

The CLOUT Registry study was designed to capture real-world data regarding the clinical use of the ClotTriever System and involves the collection of specific information for research and educational purposes only. It does not specify how the ClotTriever Thrombectomy System will be used to treat DVT, and decisions regarding a subject's treatment are not influenced by the study. This is a data collection study only; there is nothing investigational or experimental in the subject's medical treatment.

Therefore, the study will only capture AEs related to the subject's DVT condition and its treatment. Reportable AEs include all events considered in the safety analyses (i.e., major or minor bleeding, access site complications, new symptomatic PE within 30 days, or rethrombosis), all device- and/or procedure-related AEs, as well as any event resulting in death.

The AEs will be captured on the Adverse Event CRF and should include, wherever possible, severity, duration, outcome, and the Investigator's description of the event and his/her medical judgment as to the relationship of the AE (i.e., not related, related, or relationship unknown) to the study device, the index procedure or any subsequent procedure(s), to a thrombolytic agent or anticoagulant, or to underlying disease.

- Non-serious reportable AEs are to be submitted via the electronic data capture system (EDC) in a timely fashion.
- Reportable SAEs must be reported to the Sponsor within 5 business days of the Investigator's knowledge of the event. The event is reported in the electronic data capture system.

Appendix 1 includes a list of possible SAEs associated with thrombectomy, including those events considered major device-related events and major morbidity. These events are considered reportable at all time points throughout the study and require submission to the Sponsor.

10 STATISTICS AND DATA ANALYSIS

10.1 STATISTICAL METHODOLOGY

The statistical design objective for this study is to evaluate patient outcomes of the study device, as assessed in comparison to literature-derived performance goals.

The safety and effectiveness performance goals were determined from a literature review of publications on the treatment of DVT. A total of seven studies were included in this review and, among these, all publications reported data referable to the primary safety endpoint and six of the seven publications reported data referable to the primary effectiveness endpoint. Studies with populations that overlapped the population of another study were excluded. In general, these studies report data on acute and subacute DVT, but not chronic.

10.2 PRIMARY SAFETY ENDPOINT ANALYSIS

The primary safety endpoint for this study will be assessed in the Primary Analysis Safety cohort and is a composite endpoint of any MAE within 30 days, as determined by the independent Medical Monitor. The MAE is defined as the 30-day rate of all-cause mortality, major bleeding, new symptomatic PE documented by CTPA, or rethrombosis of the target venous segment(s). The rate of MAE will be compared to a performance goal with the following null and alternative hypotheses:

 H_0 : $P_s \ge PG_s$ versus H_A : $P_s < PG_s$

where Ps is the proportion of subjects free from MAE through 30 days and PG_S is the safety performance goal derived from the studies reporting the elements contained in the composite MAE endpoint.

The exact binomial one-sided 97.5% confidence interval will be used to test the primary safety endpoint.

10.3 PRIMARY EFFECTIVENESS ENDPOINT ANALYSIS

The primary effectiveness endpoint is Technical Success, defined by complete or near complete thrombus removal. Thrombus removal is determined by the Marder score at the index procedure, measured after use of the study device but prior to the use of adjunctive devices. Effectiveness will be assessed in the Primary Analysis Effectiveness Cohort^f and will be compared to a performance goal with the following null and alternative hypotheses:

 H_0 : $P_E \le PG_E$ versus H_A : $P_E > PG_E$

where P_E is the proportion of subjects with Technical Success, as defined complete or near complete removal of thrombus with the study device, defined by venographically-determined reduction of \geq 75% in the Marder score in

f This dataset was designed to exclude those subjects treated who underwent venous thrombectomy for lesions that were non-thrombotic in nature. For instance, those with non-thrombotic May-Thurner lesions that have externa compression or scar but who do not have demonstrable intraluminal thrombus. These subjects will remain in the Primary Safety Cohort and will be assessed for safety endpoints but will not be assessed for the effectiveness endpoints.

the TVSs. The effectiveness performance goal, PG_E, is Technical Success defined in the same manner, derived from the published literature.

10.4 STUDY SUCCESS CRITERIA

The study will be considered a success if both primary endpoints meet their respective performance goals. For the safety endpoint, this translates into observing a one-sided 97.5% lower confidence limit (LCL) of the point estimate below 34% and for the effectiveness endpoint, it means observing a one-sided 97.5% LCL above 30%.

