10.6 SAFETY PERFORMANCE GOAL DERIVATION

The primary safety endpoint of 30-day MAE was assessed from published studies that treated DVT with pharmacologic means or with other thrombectomy devices. The weighted average MAE rate was 23.8%. Using a 10% margin and rounding to the nearest percent, the performance goal for the primary safety endpoint, 30-day freedom from MAE, was 34%. A detailed analysis of the safety performance goal will be described in the statistical analysis plan.

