10.8 SAMPLE SIZE

The performance goal of 34% has been established for the primary safety endpoint, based on a one-sided 97.5% exact binomial test. The 30-day MAE rate is anticipated to be approximately 20%. Under this assumption, the required sample size to achieve a level of 82% power is 86 subjects (**Table 2**). Assuming 5% attrition over 30 days, enrollment of 91 subjects is necessary for the Primary Analytic Dataset.

Table 2. Sample Size - Primary Safety Endpoint

| Measure | |
|------------------------------|-------------------------------|
| Performance goal | 34% |
| Anticipated freedom from MAE | 20% |
| Significance level | .025 |
| Statistical test | One-sided exact binomial test |
| Desired power level | 82% |

| Required sample size prior to 5% 30-day attrition rate | 86 |
|--|----|
| Required sample size after attrition adjustment | 91 |

A performance goal of 30% has been established for the primary effectiveness endpoint. Anticipating an actual Technical Success rate of approximately 50%, and based upon a one-sided 97.5% exact binominal test, the required sample size to achieve a level of 97% power is 85 subjects (**Table 3**). Since the primary effectiveness endpoint is determined at the time of the index procedure, no attrition has been considered for lost to follow-up or other censoring events. However, the effectiveness endpoint is evaluated in the Primary Analytic Effectiveness cohort, and it is assumed that 3% of enrolled subjects will be treated for DVT in the absence of core laboratory-assessed visible thrombus in the TVS. Assuming a 3% attrition rate for subjects without thrombus, enrollment of 88 subjects will be necessary.

Table 3. Sample Size - Primary Effectiveness Endpoint

| Measure | |
|--|-------------------------------|
| Performance goal | 30% |
| Anticipated technical success rate | 50% |
| Significance level | .025 |
| Statistical test | One-sided exact binomial test |
| Desired power level | 97% |
| Required sample size prior to 3% attrition for subjects without thrombus | 85 |
| Required sample size after attrition adjustment | 88 |

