5.1. Sample Size

The performance goal of 34% has been established for the primary safety endpoint, based on a one-sided 97.5% exact binomial test. The 30-day MAE rate is anticipated to be approximately 20%. Under this assumption, the required sample size to achieve a level of 82% power is 86 subjects (**Table 1**).

Assuming 5% attrition over 30 days, enrollment of 91 subjects is necessary for the Primary Analytic Dataset.

Table 1. Sample Size - Primary Safety Endpoint

Measure	
Performance goal	34%
Anticipated freedom from MAE	20%
Significance level	.025
Statistical test	One-sided exact binomial test
Desired power level	82%
Required sample size prior to 5% 30-day attrition rate	86
Required sample size after attrition adjustment	91

A performance goal of 30% has been established for the primary effectiveness endpoint. Anticipating an actual Technical Success rate of approximately 50%, and based upon a one-sided 97.5% exact binomial test, the required sample size to achieve a level of 97% power is 85 subjects (**Table 2**). Since the primary effectiveness endpoint is determined at the time of the index procedure, no attrition has been considered for lost to follow-up or other censoring events. However, the effectiveness endpoint is evaluated in the Primary Analytic Effectiveness cohort, and it is assumed that 3% of enrolled subjects will be treated for DVT in the absence of core laboratory-assessed visible thrombus in the TVS. Assuming a 3% attrition rate for subjects without thrombus, enrollment of 88 subjects will be necessary.

Table 2. Sample Size - Primary Effectiveness Endpoint

Measure	
Performance goal	30%
Anticipated technical success rate	50%
Significance level	.025
Statistical test	One-sided exact binomial test
Desired power level	97%
Required sample size prior to 3% attrition for subjects without thrombus	85
Required sample size after attrition adjustment	88

The required sample size is greater for the primary safety endpoint; 91 vs. 88 subjects. Thus, a total of 91 subjects will be enrolled in the Primary Analysis dataset; providing approximately 91 subjects in the Primary Safety cohort and 88 subjects in the Primary Effectiveness cohort for the primary safety and effectiveness analyses, respectively. The overall power of the study is 80%.

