5.2. Derivation of Performance Goal

5.2.1. Derivation of the Safety Performance Goal

The primary safety endpoint of 30-day MAE was available from the following seven studies, summarized in **Table 3**.

Table 3. Safety Performance Goal Literature Summary

Study	Year	Subjects	MAE (%)
Lin	2017	89	35 (39.3%)
Vedantham	2017	336	12 (3.6%)
Schweitzer	2000	50	1 (2.0%)
Elsharawy	2002	18	0 (0%)
Enden	2011	90	13 (14.4%)
Mewissen*	1999	473	60 (12.7%)
Mewissen	1999	312	75 (24.0%)
Engelberger	2015	48	2 (4.2%)
Total		1,104†	198
Weighted Average			23.8%‡

* The second row for the Mewissen study is included to tabulate rethrombosis rate, which was specified for the 312 subjects with acute DVT alone.

†The total number of subjects does not include the 312 subjects in the acute cohort of the Mewissen publication, since this is a subset of the 473 subjects in the series.

‡The MAE weighted average was calculated individually using a random effects model for each component of the composite endpoint and then summed to derive the weighted average for the composite MAE endpoint. For this reason, the denominator for the weighted average is not 1,104, nor does the MAE weighted average represent a simple weighted average of the MAE rates of the individual publications.

The weighted average MAE rate was 23.8%. Using a 10% margin and rounding to the nearest percent, the performance goal for the primary safety endpoint, 30-day freedom from MAE, is 34%.

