5.3. Primary Safety Endpoint Analysis

The primary safety endpoint for this study will be assessed in the Primary Analysis Safety cohort and is a composite endpoint of any MAE within 30 days, as determined by the independent Medical Monitor. The MAE rate is defined as the 30-day rate of all-cause mortality, major bleeding, new symptomatic PE documented by CTPA, or rethrombosis of the target venous segment(s). The MAE rate will be compared to a performance goal with the following null and alternative hypotheses:

$$H_0: P_S \geq PG_S \text{ versus } H_A: P_S < PG_S$$

where P_S is the proportion of subjects with MAE through 30 days and PG_S is the safety performance goal derived from the studies reporting the elements contained in the composite MAE endpoint.

The exact binomial one-sided 97.5% confidence interval will be used to test the primary safety endpoint.

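### The safety success rule puts the lower confidence limit, not the upper, below 34%, and the protocol defines the tested proportion as its complement

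*Protocol*

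**What the plan says.** **Success rule.** Protocol 10.4 requires both primary endpoints to meet their goals. It then spells out the safety half: "For the safety endpoint, this translates into observing a one-sided 97.5% lower confidence limit (LCL) of the point estimate below 34"%. For effectiveness, the same sentence asks for a lower limit above 30%. The SAP has no success-criteria section. SAP 5.3 and Protocol 10.2 say only that an exact one-sided 97.5% interval will be used, without naming the side.

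**Parameter.** Both documents test H0: P_S ≥ PG_S against HA: P_S < PG_S, but they define P_S in opposite ways:
- Protocol 10.2: "where Ps is the proportion of subjects free from MAE through 30 days".
- SAP 5.3: "where P_S is the proportion of subjects with MAE through 30 days".

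**Labels.** Protocol 10.6 derives the goal from a weighted average MAE rate of 23.8% plus a 10% margin, then states that "the performance goal for the primary safety endpoint, 30-day freedom from MAE, was 34"%. SAP 5.2.1 repeats this: "the performance goal for the primary safety endpoint, 30-day freedom from MAE, is 34"%. Protocol Table 2 and SAP Table 1 give the 20% planning value under the label "Anticipated freedom from MAE", although the text above each table calls the same 20% the anticipated MAE rate.

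**Design.** Protocol 10.8: "The performance goal of 34% has been established for the primary safety endpoint, based on a one-sided 97.5% exact binomial test". The remaining figures there are significance level .025, 82% power, 86 evaluable subjects, and 91 after 5% attrition.

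**The concern.** The aim is to show that an event rate is below a ceiling. The data support that only when the whole plausible range lies under the ceiling, that is, when the upper limit is below 34%. A lower limit below 34% shows only that the data have not proved the rate to be above 34%. That is failure to reject the opposite hypothesis, and it gives no control of false success at the goal. The lower limit is the right one for effectiveness, where success means exceeding a floor. It looks as if the limit was carried over to safety and only the inequality was reversed.

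The definition of P_S in Protocol 10.2 is a second, independent fault, and it acts in the other direction. If P_S is freedom from MAE, then P_S < 34% means that more than 66% of subjects have an MAE, and a safe device fails.

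This is one of two co-primary decision rules on which study success depends. Left as it is, success could be declared at an MAE rate well above the goal, or the correct reading could be disputed after the data are known.

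**Working it through.** **Inputs.** Goal 34%, anticipated MAE rate 20%, one-sided alpha .025, exact binomial test, n = 86 evaluable and 91 enrolled (Protocol 10.8 and SAP 5.1).

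**Formulas.** With x subjects having an MAE out of n, the exact (Clopper-Pearson) one-sided 97.5% limits are
- lower: L(x) = the 0.025 quantile of Beta(x, n − x + 1)
- upper: U(x) = the 0.975 quantile of Beta(x + 1, n − x)

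If a rule passes for all x ≤ c, its pass probability at true rate p is P(X ≤ c), with X binomial(n, p).

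**Step 1: reproduce the plan's design.** Take the rule U(x) < 34% on the MAE rate, n = 86.
- U(20) = 33.6% and U(21) = 34.9%, so the rule passes for x ≤ 20 (23.3%).
- False-pass probability at p = 0.34: 2.1%, within the stated .025.
- Power at p = 0.20: 81.5%, against the stated 82%.
- Attrition: 86 / 0.95 = 90.5, rounded up to 91.
- Normal approximation at 82% power: (z₀.₉₇₅·√(0.34·0.66) + z₀.₈₂·√(0.20·0.80))² / 0.14² = 85.5, hence 86.

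The stated design is therefore an upper-limit test on the MAE rate.

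**Step 2: the rule in Protocol 10.4, applied to the MAE rate.** L(x) < 34%, n = 86.
- L(38) = 33.5% and L(39) = 34.6%, so it passes for x ≤ 38 (44.2%).

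| True MAE rate | P(pass), lower limit < 34% (x ≤ 38) | P(pass), upper limit < 34% (x ≤ 20) |
|---|---|---|
| 34% | 98.1% | 2.1% |
| 40% | 81.7% | 0.08% |
| 45% | 48.4% | < 0.01% |
| 50% | 16.6% | < 0.01% |

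If all 91 subjects are evaluable, the cut-offs are 40 and 21 events. At a true 34% the pass probabilities are 98.1% and 1.6%, and the upper-limit rule has 80.8% power at 20%.

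**Step 3: P_S read as freedom from MAE (Protocol 10.2).** n = 86; the anticipated 20% MAE rate means P_S = 80%. The result depends on which limit is used.
- Lower limit of freedom < 34% (10.2 and 10.4 taken together): passes only if at most 38 are free, that is, at least 86 − 38 = 48 MAEs (55.8%). P(pass) is about 3 × 10⁻¹³ at a true MAE rate of 20%, about 3 × 10⁻⁵ at 34%, and 98.1% at 66%.
- Upper limit of freedom < 34% (the 10.2 hypotheses tested at .025): passes only if at most 20 are free, that is, at least 66 MAEs (76.7%). P(pass) at a true MAE rate of 20% is about 1.7 × 10⁻²⁹.

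**Step 4: the freedom scale done correctly.** A lower limit of freedom above 100% − 34% = 66% requires at least 66 of 86 free, that is, at most 20 MAEs. This is the same rule as in Step 1. A 34% goal does not carry over to the freedom scale unchanged.

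**The case against.** The strongest reply is that the intended test is not in doubt. SAP 5.3 already defines P_S as the proportion with MAE, states HA: P_S < PG_S and names an exact one-sided 97.5% interval; for that alternative, only the upper limit gives a .025 test. The sample size reproduces only that way. Protocol 10.2 itself speaks of comparing the MAE rate with the goal, the endpoint sections define a rate of MAE, and the 34% comes from an MAE rate. On this view the freedom labels are slips, and this is in any case an observational registry of a cleared device.

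Much of that is right, and it makes the correction easy. It does not amend Protocol 10.4. That section is the only place where a limit is compared with the safety goal, and the SAP neither replaces it nor names a side. The SAP also keeps the freedom labels. Observational or not, the protocol specifies formal hypothesis tests and a success claim that needs both endpoints.

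Two limits on the point do stand. First, the two faults pull in opposite directions: the 38-event cut-off and the 98.1% apply when the limit is taken on the MAE rate, not on freedom. Second, the written rule can still fail a device far above the goal. It fails in about 52% of trials at a true 45% and about 83% at a true 50%. What is lost is error control at and near 34%.

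**Conclusion.** The concern holds. Applied to the MAE rate, the criterion in Protocol 10.4 has a 98.1% false-pass probability at the 34% goal, where the design promises at most 2.5%, and it accepts up to 38 of 86 events instead of 20. Under the protocol's own definition of P_S, a device performing as anticipated would have essentially no chance of success. Either fault alone makes the rule wrong as written. Only the upper limit of the MAE rate below 34%, or equivalently the lower limit of freedom from MAE above 66%, agrees with the stated alpha and power.

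The figures assume exact one-sided 97.5% limits and 86 evaluable subjects; at 91 the conclusion is the same. They take the 34% goal as given and do not assess how it was derived. This must be corrected, since it governs a co-primary decision.

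**What to change.** - **Protocol 10.4:** define safety success as the one-sided 97.5% exact upper confidence limit of the 30-day MAE rate lying below 34%.
- **SAP 5.3:** repeat that criterion in full, so that the limit and its side are stated where the test is defined.
- **Protocol 10.2:** define P_S as the proportion of subjects with an MAE through 30 days, as SAP 5.3 does. The hypotheses can then stay as they are.
- **Protocol 10.6, Protocol Table 2, SAP 5.2.1 and SAP Table 1:** replace the freedom-from-MAE label with MAE rate for both the 34% goal and the 20% expectation.
- It would help to add the resulting cut-offs to the SAP: at most 20 events if 86 subjects are evaluable, at most 21 if 91 are.

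The cost is a wording amendment to both documents, with the IRB approval that Protocol 11.2 requires for protocol changes. Sample size, data collection and the planned test are unaffected. The correction should be dated before the primary safety result is examined.
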